#### The following data will be collected once per patient

The following data should be answered in relation to the date as referenced in the list below.

Note only one date is required, please complete for the first that is applicable as working down the list

- 1. Date of screening test (if single test)
- 2. If multiple screening tests:
  - a. If any positive, date of first positive screen OR
  - b. If all negative, date of most recent screen
- 3. Today's date if never screened

Field name	Field description	Response/notes				
Patient details						
Patient ID	Unique patient ID	System generated				
*Reporting organisation	ICU name	Single select drop down				
*Date of interest	Date of interest to which exposure questions relate. In order of preference:	DD-MM-YYYY				
	1. Date of CPE screening test (if single test) 2. If multiple CPE screening tests: a. If any positive, date of first positive screen OR b. If all negative, date of most recent screen					
	3. Today's date if never screened					
*10-digit NHS number	10-digit NHS number, if not available, enter [contact]					
*Forename	Patient first name	Text				
*Surname	Patient surname	Text				
*Date of birth	Patient date of birth	DD-MM-YYYY, if not known enter 01/01/1900				
*Sex	Biological sex	Button options:				
		Male Female Unknown				
Patient details 2						
*Survey date	Date survey is conducted	DD-MM-YYYY				
*Patient age group		Single select drop-down: Adults				
		Paediatrics				
		Neonates				

Ethnicity	Ethnicity of patient	Two-stage single select drop-down
*UK resident	Indicate if patient normally resides in the UK  NB. If for a neonate, please use details of mother	Single select drop-down: Yes No Unknown
Normal country of residence if not UK		Single select drop-down
*Birthweight	Birth weight (in grams) of neonatal patients i.e. babies less than 28 days old OR on NICU.	Number in grams
*Gestation	Gestation for babies aged under 1 year	Weeks + days
*Patient category	Indicate patient category on admission	Single select drop-down: NHS Private Diplomatic Other Unknown
Other patient category	Specify patient category if "other"	Text
*Date admitted to hospital	Date admitted to the trust, or date of birth if neonate and admitted since birth	DD-MM-YYYY
*Admitted from	Setting patient admitted from into the trust	Single select drop-down:  Home  A&E International transfer Nursing home Other Trust  Non-NHS hospital Non-health-related institute Temporary accommodation Other

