Indicate which carbapenemase family was detected (select all that apply)	Indicate which carbapenemase family was detected (select all that apply)	Multiselect drop-down
If Other, specify other carbapenemase family		Text
Screening (NB no additional sc	reening is required)	
*CPE on admission to Trust	Was the patient known to be CPE positive on admission to Trust	Single select drop-down: Yes – colonised Yes - infected No Unknown
*CPE screening on admission to Trust	Found to be CPE positive on admission to Trust.  "Yes" if screening specimen positive, "no" if screening specimen negative, "unknown" if no screen performed.	Single select drop-down: Yes No Unknown
*CPE on admission to ICU	Known to be CPE positive on this admission to ICU i.e. communicated/identified at time of admission.	Single select drop-down: Yes No Unknown
*ICU screen required	Did patient meet requirement to be screened for CPE on ICU in accordance with your policy?	Single select drop-down: Yes No Unknown
*ICU admission screen	Was patient screened for CPE on this admission to ICU?	Single select drop-down: Yes No Unknown

		1
*ICU admission screen date	Date admission screen was taken on ICU	DD-MM-YYYY
*Result of ICU admission screen	Indicate result from ICU CPE admission screen	Single select drop-down: Positive Negative Unknown
*Previous CPE	Indicate if patient known to be CPE colonised/infected in 12 months prior to first day of survey	Single select drop-down: Yes – colonised Yes - infected No Unknown
If previous history of CPE, specify date of most recent positive result.	Provide date of most recent CPE positive result (prior to ICU admission screen, if taken)	DD-MM-YYYY
Previous contact with CPE	Indicate if in contact with known CPE case during this admission	Single select drop-down: Yes No Unknown
Healthcare exposure		
*UK non-NHS hospital admission in previous 12 months	Any hospital admissions to non-NHS hospitals in the previous 12 months	Single select drop-down: Yes No Unknown
Specify UK non-NHS hospital admission	Provide name(s) of non- NHS hospitals admitted to in previous 12 months	Free text
*Healthcare overseas in previous 12 months	Any hospital admissions overseas in 12 months prior to admission at Trust	Single select drop-down: Yes No Unknown
Specify healthcare abroad	List countries where overseas healthcare received in previous 12 months	Multiselect dropdown of countries

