*Healthcare worker  Travel exposure	Includes working in hospitals, care/nursing homes, hospices	Single select drop-down: Yes No Unknown
*Overseas travel in previous 12 months (if known)	Any overseas travel in 12 months prior to admission to Trust	Single select drop-down: Yes No Unknown
*Specify overseas travel	List countries travelled to in previous 12 months	Multiselect dropdown of countries
Family travel	Any family members within the same household as patient travel in the previous 12 months	Single select drop-down: Yes No Unknown
Specify family travel	List countries where family members travelled in previous 12 months	Multiselect dropdown of countries
Interventions		
*Has the patient undergone major surgery since admission to the Trust, on or prior to the date of interest?	Surgery is defined as a procedure where an incision is made (not just a needle puncture), with breach of mucosa and/or skin (not necessarily in an operating theatre). If the patient has had more than one surgery since admission, report the most recent surgery.	Single select drop-down: Yes No Unknown
*Surgery date	If yes, date of surgery	DD-MM-YYYY
*Has the patient undergone endoscopy since admission to the Trust, on or prior to the date of interest?	If yes, surgery type Undergone endoscopy during this admission, prior to date of interest	Free text  Single select drop-down:  Yes  No Unknown

*Endoscopy date	If yes, date of most recent endoscopy	DD-MM-YYYY
Endoscopy type	If yes, specify type of endoscopy	Single select drop-down:  Colonoscopy Sigmoidoscopy Upper endoscopy/ Esophagogastroduodenosc opy (EGD) Endoscopic retrograde cholangiopancreatography (ERCP) Percutaneous endoscopic gastrostomy (PEG) Other
*Is the patient currently receiving Chemotherapy	Is the patient currently receiving chemotherapy for cancer treatment, or received chemotherapy in the four weeks prior to the date of interest	Single select drop-down: Yes No Unknown
Specify chemotherapy indication (select all that apply)		Single select drop-down:  Oral, nasal and pharyngeal Oesophagus Stomach Colorectal Hepatobiliary Respiratory Larynx Lung Breast Female reproductive Prostate Testicular Renal Urinary bladder Bone and joint Melanoma Non-melanoma skin Soft-tissue sarcoma Brain Leukaemia (other than

		chronic B-cell leukaemia) Chronic lymphocytic (including hairy cell leukaemia) Other
Chemotherapy indication if other		Free text

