Start date for antimicrobial 1-5  NOTE: Field repeated up to 5 times depending on the specified number of antimicrobials taken	Start date of the antibiotic.  If the antibiotic was already given on admission to hospital, provide the date of admission.	DD-MM-YYYY.
Antibiotic stewardship 1-5  NOTE: Field repeated up to 5 times depending on the specified number of antimicrobials taken	Is antibiotic prescription in line with local guidelines	Single select drop-down: Yes No Unknown
*Antimicrobials prior to the date of interest	Indicate how many antimicrobial(s) received since admission to hospital, but stopped prior to the date of interest. If more than 5 antimicrobials were prescribed, please enter details for the most recent 5.	Single select drop-down: Yes No Unknown
*Please select the number of antimicrobials taken this admission, prior to the date of interest	Indicate if antimicrobial(s) received since admission, prior to date of interest	Single select drop-down: 1 2 3 4 5
*Antimicrobial name 1-5 (prior survey)	Select the antimicrobial received since admission, prior to date of interest	Single-select dropdown list of antimicrobials.

		1
NOTE: Field repeated up to 5 times depending on the specified number of antimicrobials taken		
*Indication for antimicrobial 1-5 (before date of interest)  NOTE: Field repeated up to 5 times depending on the specified number of antimicrobials taken	Please give indication for this/these antimicrobial (s)	CI = treatment of community-acquired infection LI = treatment of infection acquired in long-term care facility (e.g. nursing home) HI = treatment for acute hospital-acquired infection SP = surgical prophylaxis MP = medical prophylaxis O = other indication UI = unknown indication (confirmed) UNK = unknown or missing information
*CPE indication for antimicrobial 1-5 (before date of interest)	Is this antimicrobial prescribed to manage CPE?	Single select drop-down: Yes No Unknown
NOTE: Field repeated up to 5 times depending on the specified number of antimicrobials taken		
Start date for antimicrobial 1-5 (before date of interest)	Start date of the antimicrobial. If the antimicrobial was already	DD-MM-YYYY
NOTE: Field repeated up to 5 times depending on the specified number of antimicrobials taken	given on admission to hospital, provide the date of admission.	
Antibiotic stewardship 1-5 (before date of interest)	Is antimicrobial prescription in line with local guidelines	Single select drop-down: Yes

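### The date-of-interest rule is not limited to screens from the current admission, so for patients whose qualifying screen is older the in-stay exposure windows are empty

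*Protocol*

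**What the plan says.** The once-per-patient section of Protocol Appendix 1 opens with the instruction that "The following data should be answered in relation to the date as referenced in the list below". The rule appears twice with the same content, in the opening list and in the *Date of interest* field:

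- a sole screen supplies its own date;
- with several screens, "If any positive, date of first positive screen";
- failing that, "If all negative, date of most recent screen";
- last, "Today's date if never screened".

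No branch says which admission the screen must belong to, and none sets a look-back limit.

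The same form expects patients with older results. *CPE on admission to Trust* records carriers already known. *Previous CPE* reads "Indicate if patient known to be CPE colonised/infected in 12 months prior to first day of survey", and a further field takes the date of the latest earlier positive.

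Three groups of exposure items are bounded on both sides, by admission and by the date of interest. Surgery is asked as "Has the patient undergone major surgery since admission to the Trust, on or prior to the date of interest". Endoscopy has the same two bounds. For earlier antimicrobials the instruction is "Select the antimicrobial received since admission, prior to date of interest".

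The Data analysis section uses such exposures for odds ratios of CPE colonisation or infection. This serves the fourth objective, on characteristics, procedures and antimicrobial use associated with CPE.

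**The concern.** An item bounded below by admission and above by the date of interest works only if the date of interest falls on or after admission. The rule does not secure this. A screen from an earlier episode can set the date, and the survey-day branch does not help, because a patient screened only in a previous stay has been screened.

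For such a patient nothing that happened in the present stay can qualify as surgery, endoscopy or earlier antimicrobial exposure. The answer then reflects when the patient was screened, not what the patient was exposed to. If this is more common among CPE-positive than CPE-negative patients, or the reverse, the odds ratios are distorted. Few positives are expected (the Assumptions section puts prevalence below 3% and likely at 0.5-1%), so a few records carry weight.

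An analysis plan cannot repair this afterwards. Surgery and endoscopy dates are entered only when the answer is Yes, so the survey would hold no record of the in-stay event.

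**Working it through.** The plan gives no figure on this point to reproduce. The check applies the rule as written and then illustrates the effect on an odds ratio.

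**1. Length of the in-stay window.** Days = max(0, date of interest − admission date + 1). Assumed example: trust admission on 1 April 2022, survey on 20 April 2022.

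- First positive screen on 1 October 2021: −182 + 1 is negative, so 0 days.
- Only screen in an earlier stay, 15 January 2022: −76 + 1 is negative, so 0 days.
- ICU admission screen on 3 April: 2 + 1 = 3 days.
- Never screened: 19 + 1 = 20 days.

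With 0 days, Yes is never logically correct, whatever happened in the stay.

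**2. Other items set beside the rule.**

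- Device items and antimicrobials taken on the date of interest would describe a day in another episode.
- The four-week and one-year carbapenem and cephalosporin items keep their length but cover the time before the old screen.
- The antimicrobial start-date field asks for the admission date if the drug was already being given on admission. With a pre-admission date of interest, the recorded start would fall after the day on which the drug is said to have been taken. This field therefore presupposes an in-stay date.
- *ICU admission screen* is expressly limited to the present ICU admission. The form sets such a limit there but not in the date-of-interest rule.

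**3. Effect on an odds ratio.** Let p1 and p0 be the true exposure proportions in CPE-positive and CPE-negative patients, and f1 and f0 the shares with an empty window, all answered No. Then

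apparent OR = odds(p1 × (1 − f1)) / odds(p0 × (1 − f0)), with odds(x) = x / (1 − x).

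The protocol gives none of these inputs. Assume p0 = 0.40, so p1 = 0.40 for a true OR of 1 and 0.571 for a true OR of 2. Example with f1 = 30%, f0 = 5% and true OR 1: 0.40 × 0.70 = 0.28, odds 0.389; 0.40 × 0.95 = 0.38, odds 0.613; ratio 0.63.

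| f1 | f0 | True OR 1 | True OR 2 |
|---|---|---|---|
| 20% | 5% | 0.77 | 1.37 |
| 30% | 5% | 0.63 | 1.09 |
| 50% | 5% | 0.41 | 0.65 |
| 20% | 20% | 1.00 | 1.79 |
| 5% | 20% | 1.30 | 2.52 |

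With p0 = 0.30 or 0.50, the 30%/5% case under no association gives 0.67 or 0.60.

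**4. Number of records involved.** Adult option 3 has 767 patients. At 1% prevalence, 767 × 0.01 = 7.7, about 8 positives. One affected positive is then 1/8 = 12.5% of the cases, and four are 50%.

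**5. Sampling error for comparison.** With 8 positives, 759 negatives and 40% exposure in both, SE(log OR) = √(1/3.2 + 1/4.8 + 1/303.6 + 1/455.4) = 0.725. The 95% interval around an OR of 1 is exp(±1.96 × 0.725), about 0.24 to 4.1, ignoring clustering.

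**The case against.** The strongest reply is that an in-stay date is plainly meant. The dependent items and the antimicrobial start-date field make sense only on that reading, earlier positives have their own fields, and the Training section promises user guides that may settle the matter. This has force as to intent. But the two statements of the rule are what sites receive, and their wording about never having been screened and about the first positive points to the patient's whole history. If some staff assume the current stay and others follow the text, sites apply different rules.

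A second reply is that exposures should precede acquisition, so No is right for an old carrier. The principle is sound, but that patient has no time at risk in this stay, and coding No compares an empty window with a full one. Nor does the reply cover patients last screened negative in an earlier stay.

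A third reply is that affected records can be found from the date of interest and the hospital admission date and then dropped or set to missing. They can be found, but their in-stay exposures were never recorded. Linkage is not a safe rescue, since the Information collected section says that data obtainable by reliable linkage were already left out of the questions.

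A reader might infer more: that every since-admission exposure is forced to No for all known carriers, and that the odds ratios are therefore pulled below 1. The document does not support this:

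- Unknown can be selected, so No follows from logic and is not forced by the system.
- The item on contact with a CPE case during this admission has no date-of-interest cut-off.
- Carriers known only from clinical isolates, or first screened positive in this stay, are not affected.
- The protocol does not say whether an earlier carrier not retested in this stay counts as a case. The laboratory section treats patients without a CPE result as negative, so affected carriers could fall among the non-cases.

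**Conclusion.** The point holds as a fault in a stated data definition. Applied literally, the rule gives a pre-admission date of interest to any patient whose qualifying screen belongs to an earlier episode. Surgery, endoscopy and earlier antimicrobials then have no window, and the device and current-antimicrobial items describe another episode.

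Only the risk-factor odds ratios are at stake; the prevalence estimates are untouched. No direction can be asserted. Under the assumed shares, an absent association could appear as anything from 0.41 to 1.30, and a true odds ratio of 2 as anything from 0.65 to 2.52. Under no association the distortion vanishes only if both groups are affected equally; with a true odds ratio of 2, equal shares of 20% still shrink it to 1.79. With about 8 adult positives these shifts lie within the sampling error shown above, so the results may not reveal the bias. That is a reason to remove it at data collection.

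**What to change.** In both places in Appendix 1 where the rule stands, limit it to screens taken during the current trust admission, and use the survey date for patients not screened during that admission. Add a check in the data capture system that the date of interest is not before *Date admitted to hospital*. Leave earlier positives in *Previous CPE* and *CPE on admission to Trust*.

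The wording change alone would create a different problem. For a carrier colonised before admission, an in-stay or survey-day date would count exposures after colonisation as risk factors. The Data analysis section should therefore exclude patients known to be CPE-positive on admission from the main analysis of in-stay exposures, or analyse them separately, and not leave this to a sensitivity check.

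The cost is two wording changes, one validation rule and an exclusion based on a mandatory field already on the form. The downside is fewer cases in that analysis, where few are expected to begin with.

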# Study design

A prospective, cluster randomised cross-sectional survey approach will be used to provide estimates of prevalence of CPE for clinically indicated samples and rectal screening (stool sample or rectal swab) isolates from the randomly selected acute trusts.

Samples taken for routine clinical management purposes from the selected patients (e.g. blood, urine, wound) will be included, as will rectal screening (stool sample or rectal swab) taken to determine if the patient is colonised with a CPE.

The selected patients receiving in-patient treatment in the participating trusts' units will be included in the survey on the survey date. A single survey day will be used for each trust to minimise the workload for the clinical teams and to optimise sample collection.

Intensive care ward staff will implement the survey by randomly selecting patients and providing relevant data for the survey. To ease the workload, an online survey tool will be used for data collection purposes. ICU staff will be advised on methods of randomly selecting patients within the ward; the method by which patients are selected will be dictated by the number of critical care beds.

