#### Sampling patients

Patients in each included trust are to be selected at random by the NHS staff conducting the study. All patients should have an equal opportunity for selection regardless of their known or suspected infection or colonisation status. It is anticipated that collecting data on up to 20 patients will be manageable in the one-day survey period. Trusts with fewer than 20 ICU patients will be asked to include all of their patients, those with more will be asked to select a random sample of 20.

Trusts with more than one ICU for the relevant age group should sample patients at random from across all their units.

Guidance will be provided on how to randomly select patients, for example:

As first preference, and for an ICU with any number of beds:

 Use a random number generator to obtain a list of 20 bed numbers to sample e.g. https://www.random.org/

If a random number generator cannot be used:

For an ICU with approximately 40 patients:

- 1. Flip a coin to pick whether to start with bed 1 or 2
- 2. Sample every other bed

For an ICU with approximately 60 patients:

- 1. Draw lots to pick whether to start with bed 1, 2, or 3
- 2. Sample every third bed

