# Data collection

Data collection from patient records will be carried out by hospital staff, using a digital data collection system, adapted from the HCAI Data Capture System (DCS) used for ICCQIP and the mandatory surveillance of healthcare associated infections. Some additional data will be collected through linkage to Hospital Episodes Statistics. It is anticipated that the data collection will primarily be done by staff on the ward being surveyed, but it is also possible that infection prevention and control could also be brought in to assist with the survey process.

 Patients are recruited from a single day. However, there will be two weeks available following the study date for trusts to enter the data.

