#### Data collection procedure

To minimise burden on clinical staff and to reduce time required for data analysis, it is proposed an online data collection system (DCS) will be used for this survey. This is already in use for ICCQIP. However, it is acknowledged that it may not be practical for staff to enter data directly while collecting data into the web-based tool, and therefore a printable version of the survey, which can be completed and data subsequently entered into the DCS, will be provided.

The HCAI/AMR team located at Colindale will provide the repository for the data and only key members of survey team will have access to that data, for all ICUs. A line listing report will be available for participating trusts to access and download their data; no data from other trusts will be available via the DCS.

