Other admitted from	Specify if admitted from "other" location	Text

*Date admitted to ICU	Date admitted to ICU	DD-MM-YYYY
Time admitted to ICU	Specify time admitted to ICU	HH:MM (24-hour clock)
*Location admitted to ICU from	Setting patient admitted from into ICU	Single select drop-down: Home A&E HDU within same Trust Other ward within same Trust International transfer Nursing home Other Trust
		Non-NHS hospital Non-health-related institute Temporary accommodation Other Unknown
Other admitted from (ICU)	Specify if admitted to ICU from "other" location	Text
*If admitted to ICU from another ward within the same Trust, please specify	Specify specialty patient was admitted into the ICU from	Single select drop down Adult Paeds Neonates Other
If other, please specify	Specify other/specialty	Text
Please specify Adult speciality		
 
General medical
 
General surgical
 
Specialty
 
Intensive care
 

Please specify Paeds speciality		

Medical

Surgical

Specialty

Intensive care

		

Surgical

Specialty

	Γ	T
If 'Speciality', please specify which Paeds speciality	Specify other/specialty	Text
If 'Speciality', please specify which Neonatal speciality	Specify other/specialty	Text
APACHE II score	Score measures severity of disease for patients admitted to ICUs. Provide score assigned to patient on admission to ICU	Integer, ranging 0 - 71
Microbiology details		
*Was this patient tested for CPE, either as screening or as part of clinical investigations?		Single select drop-down: Yes No Unknown
*Was it a screening or clinical specimen?	Indicate if screening specimen or clinical specimen	Single select drop-down: Screening Clinical Unknown
*Date CPE specimen collected	Date specimen collected (if single specimen). If multiple specimens, please provide the most recent date.	DD-MM-YYYY
Specimen/laboratory number assigned to specimen		Free text
Indicate anatomical site specimen collected if clinical specimen		Single select drop-down
*Organism	Organism isolated associated with CPE positive result. If no result yet, select "Unknown/result awaited". If no organism isolated, select "No organism isolated".	Single select drop-down

	T	T
Does phenotypic testing indicate the presence of a carbapenemase?	Indicate if phenotypic (antibiotic susceptibility) testing indicates presence of a carbapenemase	Single select drop-down: Yes No Unknown

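### The survey form does not tie CPE specimens or the date of interest to the survey day, so a form completed late can take in specimens and exposures from after it

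*Protocol*

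**What the plan says.** **What is tied to the survey day.** Under Patients, eligibility depends on being on the ward at 8am. Study design states "A single survey day will be used for each trust", and footnote 1 under Data collection adds "Patients are recruited from a single day".

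**What is not tied to it.**
- Study design: "Samples taken for routine clinical management purposes from the selected patients (e.g. blood, urine, wound) will be included". Rectal screens are included too. No earliest or latest collection date is given for either.
- Appendix 1, once-per-patient section: the date of interest is the date of the single screen. With several screens it is the first positive or, if all are negative, the latest. Otherwise it is "Today's date if never screened". Survey date is a separate mandatory field, and nothing says that today means the survey date.
- Appendix 1, Microbiology details: "If multiple specimens, please provide the most recent date".
- Information collected: microbiology results may be linked from another surveillance system, with no date window.

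**Time allowed.** Footnote 1 says "there will be two weeks available following the study date for trusts to enter the data". Data collection describes hospital staff taking data from patient records using the digital system. Data collection procedure also offers "a printable version of the survey, which can be completed and data subsequently entered into the DCS".

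**The concern.** A point prevalence needs one reference time for both denominator and numerator. Here the denominator has one (8am on the survey day) and the numerator has none in writing. Staff who open the record a week later and follow the instructions as printed would pick the latest specimen then on file. The once-per-unit section lists weekly and outbreak screening among the options, so further specimens in that week are plausible in some units.

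Two things are at stake. First, the recorded CPE result could depend partly on how late a trust completes its forms and how often it re-screens. Both can differ between trusts, and the Data analysis section plans estimates by stratum. Second, the device, surgery and antimicrobial questions are asked relative to the date of interest. For never-screened patients that date could fall after the survey day, which would blur the risk-factor comparison.

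**Working it through.** **1. Following the form literally.** These are constructed examples; day 0 is the survey day.

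| Patient | Form completed | Literal result | If limited to day 0 |
|---|---|---|---|
| No test by day 0; first screen day 5, positive | day 0 | date of interest day 0; no result, so assumed negative (Laboratory specimen section) | same |
| Same patient | day 10 | date of interest day 5; positive | date of interest day 0; assumed negative |
| Clinical specimen positive day -2, another negative day 5 | day 10 | specimen date is day 5; the day -2 specimen is displaced from that item | specimen date day -2 |
| Never screened | day 12 | date of interest day 12 | date of interest day 0 |

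The third row shows that the error need not always raise prevalence.

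**2. Can analysis repair it?** Partly. Survey date, date of interest and specimen date are all mandatory, so a late specimen is visible and can be excluded. But the form asks for only one specimen date, so a displaced specimen may not be on it. Exposures cannot be fully re-anchored either. For example, urinary catheter use is asked for the date of interest and, if absent, for the preceding 48 hours. A catheter in place on day 0 and removed on day 4 is not captured when the date of interest is day 12.

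**3. Scale of the adult sample.** The plan's own figure first, using the precision formula with finite population correction:

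n = DEFF × N × p(1−p) / [(d²/z²)(N−1) + p(1−p)]

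Inputs from Sample size and Assumptions: N = 4090 beds, p = 0.01, d = 0.01, 95% confidence (z = 1.96), DEFF = 2, plus 10%.

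n = 2 × 4090 × 0.0099 / [(0.0001/3.8415) × 4089 + 0.0099] = 696.1, rounded up to 697. Then 697 × 1.1 = 766.7, which reproduces the stated 767.

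Without the 10% allowance, 767/1.1 = about 697 completed forms. At 1% that is about 7 cases. One extra case adds 1/697 = 0.14 percentage points, against a planned precision of ±1 point.

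**4. Illustration only.** The protocol gives no detection rates, so all rates here are assumed. Let L be the extra days during which specimens are picked up, and λ the new detections per 1000 patient-days. Assume every patient stays under observation:

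recorded prevalence = p + (1−p)(1 − exp(−λL/1000)), with p = 1%

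| L (days) | λ = 0.1 | λ = 0.5 | λ = 1 |
|---|---|---|---|
| 0 | 1.00% | 1.00% | 1.00% |
| 3 | 1.03% | 1.15% | 1.30% |
| 7 | 1.07% | 1.35% | 1.69% |
| 14 | 1.14% | 1.69% | 2.38% |

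In 697 forms the non-zero rows correspond to 0.2 to 9.6 extra recorded cases. A scenario with two extra weekly screens, 30–50% of patients still on the unit and 0.25–0.5% newly detected per screen gives 0.01 + 2 × 0.3 × 0.0025 = 1.15% to 0.01 + 2 × 0.5 × 0.005 = 1.5%. Both ranges are set by their assumptions and shrink to 1% when forms are completed on the survey day.

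**The case against.** A reader might infer that the protocol counts tests taken after the survey day, and so estimates an inflated period prevalence. The documents do not support that:

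- No text says later specimens count. The two weeks are described as time to enter data, and Sampling patients expects that "collecting data on up to 20 patients will be manageable in the one-day survey period". A paper form completed that day and typed in later avoids the problem. The option to record a result as still awaited also fits completion near the survey day.
- The today's-date rule applies only to never-screened patients and sets the date for exposure questions, not case status. It cannot by itself make a later test count. The specimen problem rests on the most-recent-specimen rule and the unbounded screening rules.
- Inflation relative to true carriage is not shown. The aim is the prevalence of infection and colonisation, and a positive on day 5 may reveal carriage already present on day 0. Counting untested patients as negative pulls the estimate down.
- A relative increase of 15–50%, as in the weekly-screen scenario, is correct arithmetic on assumed inputs. It leaves out the zero case and takes weekly screening as given, although weekly is only one option on the unit form.
- The window is open backward as well: no earliest date is stated for a first positive screen or a specimen.

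All of this stands, and it limits the point to what the form permits. It does not remove the point. The printable form is an option rather than a requirement, today is not defined, and the same form refers explicitly to the day of the survey elsewhere (bed occupancy, surgical prophylaxis). Leaving the repair to the analysis works only in part.

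**Conclusion.** The point holds as a gap in the collection rules. Read literally on a late form, Appendix 1 can record a specimen collected after the survey day, displace an earlier specimen, and date the exposures of never-screened patients after the survey day. The point prevalence can then depend partly on entry delay and re-screening frequency.

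The size is unknown. It is zero where forms are completed on the survey day. Elsewhere it depends on completion delay, re-screening and detection rates that the protocol does not give. With about 7 expected adult cases at the planned 1%, even a few late detections would be visible in the estimate. The change is worth making before data collection because later analysis cannot fully recover what the form did not ask for.

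**What to change.** In Appendix 1, once-per-patient section:

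1. Replace "Today's date if never screened" with the survey date, in both the introductory list and the date-of-interest field.
2. Limit the screening rules (single, first positive, most recent) to specimens collected on or before the survey date.
3. Limit the specimen-date item to the most recent specimen collected on or before the survey date.

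For all these items, accept results that are reported during the two-week entry period. State the earliest collection date that counts as well, so that the window is closed at both ends, and apply the same window to linked microbiology under Information collected. Have the data capture system reject a specimen date or date of interest later than the survey date.

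The cost is three wording changes and one validation check, with the window stated once for the linkage. No extra sampling, data items or staff are needed, and the sample size stays at 767 for adults.
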